7. DISCONTINUATION OF STUDY INTERVENTION AND PARTICIPANT DISCONTINUATION/WITHDRAWAL

7.1. Discontinuation of Study Intervention

Participants may voluntarily withdraw from the study at any time and for any reason. Site investigators and study staff may withdraw participants before their scheduled termination visit for safety, behavioural, or administrative reasons, or if the participants are unable or unwilling to comply with study procedures. The reasons for withdrawals will be recorded in the participants' study records. If a participant withdraws from the study, he/she may request destruction of any samples taken, and the investigator must document this in the site study records.

During the oral lead-in period, early withdrawal on medical grounds will occur if the participant develops a grade 3 or higher AE that is judged by the investigator to be related

directly to the study product (see [Appendix 3](#) and [Appendix 4](#) for definitions and grading of severity of adverse events), or any AE that is deemed clinically significant by the investigator and is judged by the investigator to be related directly to the study product.

For liver-related stopping criteria, please refer to Section [7.1.1](#).

During the oral lead or injection phase additional pre-specified reasons for discontinuing a participant from the study (or, at minimum, discontinuing administration of study product and continuing safety evaluations) include:

- Pregnancy (please see Section [8.3.5](#))
- Protocol deviation
- Non-compliance
- Participant withdraws consent
- Participant lost to follow-up
- Investigator discretion
- Sponsor discontinues study

During the injection phase of the study reasons for discontinuing study intervention for a participant are outlined below:

- Any participants experiencing a grade 3 or higher AE event prior to the follow-up phase will withdraw from study intervention and enter the follow-up phase if i) the AE is considered related to IP in the opinion of the investigator and sponsor and ii) the investigator and sponsor agree the subject should be withdrawn from study intervention or
- Any participant developing a grade 3 or higher laboratory abnormality (with the exception of asymptomatic Grade 3 or higher cholesterol, triglyceride or CPK increase) prior to the follow-up phase and the investigator and sponsor agree the participant should be withdrawn from study intervention or
- Any participant developing a grade 2 or higher rash with concurrent fever, AST/ALT elevation or eosinophilia prior to the follow-up phase will be withdrawn from study intervention.

During the injection phase of the study, reasons for pausing recruitment or dosing of a cohort following review of safety data or Study Team Review are outlined below. Approval to recommence recruitment to or dosing of a cohort following a pause would be given by the ViiV Healthcare Safety and Labelling Committee (VSLC). In the event of a pause of dosing in the injection phase, the washout period may be extended if deemed necessary by the investigator and sponsor.

- 25% of participants receiving GSK1265744 have a grade 3 or higher AE or laboratory abnormality (with the exception of asymptomatic Grade 3 or higher cholesterol, triglyceride or CPK increase) prior to the follow-up phase or a \geq Grade 2 rash with concurrent fever, AST/ALT elevation or eosinophilia prior to the follow-up phase, where the AEs are considered related to IP in the opinion of the investigator and sponsor.

- If greater than 40% of injections administered within a single cohort are followed by a local injection site reaction of at least grade 2 in severity (once half of cohort participants have received one or more injections).¹⁷
- If $\geq 20\%$ of injections given within a single cohort are followed by an injection site reaction of at least grade 3 in severity (once half of cohort participants have received one or more injections).¹⁷
- If liver chemistry stopping criteria (see Section 7.1.1) are met in a participant in Cohort 5/6.
- If a Cohort 5/6 participant has abnormal liver chemistries not meeting protocol-specified stopping rules, the investigator believes study intervention discontinuation is in the best interest of the participant.
- If a Cohort 5/6 participant develops a grade 2 or higher rash with concurrent fever, AST/ALT elevation or eosinophilia prior to the follow-up phase and is withdrawn from study intervention.

During the long acting phase of the study reasons for stopping the study following Study Team Review are outlined below:

There is a participant death assessed as related to study drug by the principal investigator and sponsor.

If a participant is withdrawn prior to receiving the CAB LA injection, a follow-up/withdrawal visit should be scheduled 10-14 days after the last oral dose of CAB. If study intervention is definitively discontinued during the injection phase, the participant will remain in the study and be followed 52-weeks post last injection per the SoA or until CAB is undetectable for appropriate procedures, including blood plasma PK sampling, and safety evaluations, and will not be removed from the study for medical reasons, unless they withdraw consent to continue participation.

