4.1.6. Follow-up/Withdrawal Visit

Because of the long acting PK profile of CAB 400 mg/mL and 200 mg/mL LA, every effort should be made to bring participants back over the 52-week follow-up phase after the last injection.

Part 1, all participants, who received CAB 400 mg/mL or 200 mg/mL LA injections, will return to clinic for safety and PK assessments at Weeks 4, 8, 12, 20, 28, 36, 44 and 52 post last IM and SC injection or until the drug level of CAB is below the level of quantification if this occurs prior to Week 52.

Part 2, Cohort 5/6 participants, who received CAB 400 mg/mL or CAB 200 mg/mL LA injections, will return to clinic for safety and PK assessments at Weeks 12, 24, 40 and 52 post last injection or until the drug level of CAB is below the level of quantification if this occurs prior to Week 52.

If a participant is withdrawn prior to receiving any injection, then a follow-up/withdrawal visit should be scheduled 10-14 days after the last oral dose of CAB. If a participant is withdrawn or disqualified from the study after receiving at least one injection of CAB LA, because of the long acting PK profile of CAB, every effort should be made to bring the participant back in for the 52 weeks of safety and PK assessments following the last injection at weeks post injection as outlined in the SoA or until the drug level of CAB is below the level of quantification if this occurs prior to Week 52. Participants who terminate before week 52 post last injection will be asked to return to the site for a withdrawal visit.

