Note: A heart rate from 100 to 110 bpm can be rechecked by ECG or vitals within 30 minutes to verify eligibility.

22. Evidence of previous myocardial infarction (does not include ST segment changes associated with re-polarization).

23. Any conduction abnormality (including but not specific to left or right complete bundle branch block, atrioventricular [AV] block [2nd degree or higher], Wolff-Parkinson-White [WPW] syndrome).
24. Sinus Pauses > 3 seconds.
25. Any significant arrhythmia which, in the opinion of the Investigator OR GSK/ViiV Healthcare Medical monitor, will interfere with the safety for the individual participant.
26. Non-sustained or sustained ventricular tachycardia (≥ 3 consecutive ventricular ectopic beats).
27. Positive human immunodeficiency virus (HIV) antibody/antigen test (HIV-1 \pm HIV-2). Participants will be advised regarding safer sex. In the event a participant acquires HIV during the course of the study they will be required to withdraw from the study and will be referred urgently to an HIV treatment centre for further management.
28. Regular use of known drugs of abuse

Other Exclusions

29. Regular use of tobacco- or nicotine-containing products within 3 months prior to screening.
30. History of sensitivity to any of the study medications, or components thereof or a history of drug or other allergy that, in the opinion of the Investigator or Medical Monitor, contraindicates their participation.
31. Participants with a history of intolerance to or with contraindications to the use of **CCI** will be excluded from participation in Cohort 4b
32. Regular alcohol consumption within 6 months prior to the study defined as:
 - a) An average weekly intake of >14 units for males or >7 units for females. One unit is equivalent to 8 g of alcohol: a half-pint (~240 ml) of beer, 1 glass (125 ml) of wine or 1 (25 ml) measure of spirits.
33. Urinary cotinine levels indicative of smoking or history or regular use of tobacco- or nicotine-containing products (e.g. nicotine patches or vaporizing devices) within 6 months prior to screening.
34. The participant has a tattoo or other dermatological condition overlying the location of injection or a prior history of silicone implants (gluteal) which may interfere with interpretation of injection site reactions or administration of CAB LA.

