7.2. Participant Discontinuation/Withdrawal from the Study

- A participant may withdraw from the study at any time at his/her own request or may be withdrawn at any time at the discretion of the investigator for safety, behavioural, compliance or administrative reasons. This is expected to be uncommon.
- At the time of discontinuing from the study, if possible, an early discontinuation visit should be conducted, as shown in the SoA. See the SoA for data to be collected at the time of study discontinuation and follow-up and for any further evaluations that need to be completed.
- The participant will be permanently discontinued both from the study intervention and from the study at that time.
- If the participant withdraws consent for disclosure of future information, the sponsor may retain and continue to use any data collected before such a withdrawal of consent.
- If a participant withdraws from the study, he/she may request destruction of any samples taken and not tested, and the investigator must document this in the site study records.

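### The protocol gives inconsistent rules on whether a participant who has received a CAB LA injection stays in the study after a safety event or HIV acquisition

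*Protocol*

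**What the plan says.** - **Section 7.1, closing paragraph.** The trigger is "If study intervention is definitively discontinued during the injection phase". The consequence is that "the participant will remain in the study and be followed 52-weeks post last injection per the SoA or until CAB is undetectable", and that such participants "will not be removed from the study for medical reasons, unless they withdraw consent to continue participation".
- **Section 7.1, opening paragraph.** "Site investigators and study staff may withdraw participants before their scheduled termination visit for safety, behavioural, or administrative reasons".
- **Section 7.2.** A participant "may be withdrawn at any time at the discretion of the investigator for safety, behavioural, compliance or administrative reasons". The section expects this to be rare, asks for an early discontinuation visit where possible, and refers to the SoA for data to be collected. It then states: "The participant will be permanently discontinued both from the study intervention and from the study at that time".
- **Section 5.2, criterion 27.** "In the event a participant acquires HIV during the course of the study they will be required to withdraw from the study".
- **Section 2.3.1, risk table, row on injection sites.** A participant with a related adverse event of grade 3 or higher, where investigator and sponsor agree, is to leave the study and go into the follow-up phase. Section 7.1 has the same rule, but the participant leaves study intervention.
- **Section 4.1.6.** For someone withdrawn or disqualified after at least one injection, "every effort should be made to bring the participant back in for the 52 weeks of safety and PK assessments". The section then asks those who terminate before Week 52 to attend one withdrawal visit. Footnote 1 of each injection-phase SoA table mentions only that visit.
- **SAP 8.1.4 and 10.7.1.** Missing PK data are not imputed. Available data from withdrawn participants are listed, and planned data are summarised.

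**The concern.** Stopping a drug and leaving a study are different events. With a long-acting injection the difference matters, because exposure continues after dosing stops; Section 4.1.6 gives the long PK profile as its reason for 52 weeks of follow-up. If one site applies the end of 7.1 and another applies 7.2 to the same event, the first collects data to Week 52 and the second may collect one visit. The SAP does not fill the gap.

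Data lost after a withdrawal for medical reasons would plausibly be related to outcome. In the HIV case, Section 2.3.1 lists resistance under waning CAB concentrations as a theoretical risk, and the participant in whom it could arise is the one criterion 27 takes out of the study.

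**Working it through.** The plan gives no figure on this point, so there is nothing to reproduce or recalculate. The check sets the rules side by side for each situation.

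| Situation after an injection | Rule pointing to staying | Rule pointing to leaving | Kind of conflict |
|---|---|---|---|
| Injections definitively stopped in the injection phase; HIV acquired | 7.1 closing paragraph (mandatory) | Criterion 27 (mandatory) | Direct: a site cannot obey both |
| Injections definitively stopped in the injection phase for a safety event | 7.1 closing paragraph (mandatory) | 7.2 and 7.1 opening (discretionary) | Prohibition against permission |
| Related adverse event of grade 3 or higher | 7.1: off study intervention, into follow-up | 2.3.1: off study, into follow-up | Same destination, different status |
| Safety event or HIV acquisition in the follow-up phase, injections completed | 4.1.6 (best effort) | 7.2 (discretionary) or criterion 27 (mandatory) | No firm rule on continued data collection |

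1. **Can the first row arise?** Yes. The SoA for Cohorts 1-4 places an HIV test before dosing on Day 1 of each injection, at follow-up Week 4 and at Week 52. If a positive result before Injection 2 ends dosing, both mandatory rules apply.
2. **Does the third row matter if the destination is the same?** It does, because calling the event study withdrawal leads the site to 7.2, which ends participation.
3. **Does 4.1.6 settle the matter?** Only in part. It addresses the right participants, but it asks for effort and then provides a single visit for those who terminate early. Neither 7.2 nor criterion 27 refers to it.
4. **Which data are exposed?** Events already under way are largely protected. Section 8.3 keeps the investigator responsible for events that led to discontinuation, 8.3.3 follows SAEs and ISRs to resolution or stabilisation, and Appendix 6 does the same for liver events. The exposed data are the scheduled laboratory, ISR and PK assessments, and new events: under 8.3.1 the investigator need not actively look for these once participation has ended.
5. **How far does this reach the PK summaries?** SAP 8.1.5 summarises follow-up concentrations by visit in Cohorts 1-4 and 4b only for participants given both injections. Someone stopped after Injection 1 in those cohorts is outside that summary whatever 7.2 says. The summary can be affected by participants who leave after both injections, and by participants in Cohorts 4h and 5, where Injection 1 alone qualifies. Plots and listings use all follow-up concentrations.

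**The case against.** The strongest reply is that the protocol already separates the two events where it counts. The named injection-phase triggers all mean withdrawal from study intervention: grade 3 or higher adverse events and laboratory abnormalities, and rash with systemic signs (7.1), liver chemistry (7.1.1) and QTc (7.1.2). Those participants fall under the closing paragraph of 7.1 and are retained. Section 7.2 is a residual, discretionary route expected to be uncommon. Section 4.1.6 speaks directly to participants withdrawn after an injection. HIV acquisition should be rare, since criterion 14 excludes participants at increased risk.

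Most of this stands, and it limits the point. A reader might infer that 7.2 and criterion 27 together remove injected participants with the worst outcomes, so that the safety summaries are flattered. The documents do not support that. Section 7.2 permits withdrawal and does not require it; only criterion 27 compels it, for HIV acquisition alone. The retention rule in 7.1 covers those whose intervention was stopped in the injection phase, not every injected participant. Participants who meet the named safety triggers are mainly those the protocol keeps.

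The reply does not remove the direct conflict between criterion 27 and 7.1, the unqualified sentence in 7.2 that ends participation, or the mismatch between 2.3.1 and 7.1. A best-effort request with a one-visit fallback does not override them.

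**Conclusion.** The inconsistency is real and should be corrected. There is one direct contradiction (7.1 against criterion 27), one conflict between a prohibition and a permission (7.1 closing paragraph against 7.2 and the opening of 7.1), and one mismatch of terms (2.3.1 against 7.1). Section 4.1.6 softens the result without curing it. Post-injection safety and PK follow-up can stop early in some participants withdrawn for medical reasons.

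No size can be given. The documents state no count or rate of such withdrawals, and neither the magnitude nor the direction of any bias can be computed. Two shortcuts may tempt a reader. The gap between enrolled and evaluable numbers is not a withdrawal rate: evaluable refers to data after both injections, and in Cohorts 1-4b randomisation precedes the oral lead-in, so the gap can include people never injected. Nor do the simulated troughs in Protocol Table 3 help, since they describe drug still in the body and not data lost.

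The conclusion rests on the wording of the protocol and SAP alone. A study reference manual might give sites a working rule, but it is not among the documents.

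**What to change.** Reconcile the 2.3.1 risk table, 4.1.6, criterion 27 in 5.2, 7.1 and 7.2, with footnote 1 of the injection-phase SoA tables, so that stopping study intervention and leaving the study are distinct throughout. Specifically:

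- Use one term for the grade 3 rule in 2.3.1 and 7.1.
- Have 7.2 and criterion 27 cross-refer to 4.1.6 and 7.1.
- State in 7.2 and criterion 27 which scheduled safety, ISR and PK data collection continues for an injected participant who has not withdrawn consent.

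No view is offered on which clinical withdrawal rule is right, or on care after HIV acquisition; the request is only that the passages agree and that the data-collection consequence is explicit.

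The cost is wording in a protocol amendment. The visits already exist in the SoA, so none need be added. The SAP methods need no change: its planned disposition and discontinuation tables (1.3 and 1.5) and the matching listings (3 and 4) can show how many participants were affected.

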7.1.1. Liver Chemistry Stopping Criteria

Liver chemistry stopping, and increased monitoring criteria have been designed to assure participant safety and evaluate liver event etiology ([across oral and injection phases] in alignment with the FDA premarketing clinical liver safety guidance).

[figure not shown]
<http://www.fda.gov/downloads/Drugs/GuidanceComplianceRegulatoryInformation/Guidances/UCM174090.pdf>

Discontinuation of study intervention for abnormal liver tests is required when:

¹⁷ Where a cohort includes administration via different routes, the ISR data will be considered by each route of administration.

- a participant meets one of the conditions outlined in the algorithm
- in the presence of abnormal liver chemistries not meeting protocol-specified stopping rules, the investigator believes study intervention discontinuation is in the best interest of the participant.

Liver Chemistry Stopping Criteria – Liver Stopping Event Algorithm

Abbreviations: ALT = alanine transaminase; INR = international normalized ratio; SAE = serious adverse event; ULN = upper limit of normal.

Refer to [Appendix 6](#) for required Liver Safety Actions and Follow up Assessments.

7.1.2. QTc Stopping Criteria

- The *same* QT correction formula *must* be used for *each individual participant* to determine eligibility for and discontinuation from the study. This formula may not be changed or substituted once the participant has been enrolled.
- For example, if a participant is eligible for the protocol based on QTcB, then QTcB must be used for discontinuation of this individual participant as well.
- Once the QT correction formula has been chosen for a participant's eligibility, the same formula must continue to be used for that participant for all QTc data being collected for data analysis. Safety ECGs and other non-protocol specified ECGs are an exception.
- The QTc should be based on the average of triplicate QTc values ECG readings obtained over a brief (less than 6 minutes) recording period (see Section [8.2.3](#)).

A participant that meets either bulleted criteria below will be withdrawn from study intervention.

- QTc >500 msec
- QTc increase from baseline >60 msec

7.2. Participant Discontinuation/Withdrawal from the Study

- A participant may withdraw from the study at any time at his/her own request or may be withdrawn at any time at the discretion of the investigator for safety, behavioural, compliance or administrative reasons. This is expected to be uncommon.
- At the time of discontinuing from the study, if possible, an early discontinuation visit should be conducted, as shown in the SoA. See the SoA for data to be collected at the time of study discontinuation and follow-up and for any further evaluations that need to be completed.
- The participant will be permanently discontinued both from the study intervention and from the study at that time.
- If the participant withdraws consent for disclosure of future information, the sponsor may retain and continue to use any data collected before such a withdrawal of consent.
- If a participant withdraws from the study, he/she may request destruction of any samples taken and not tested, and the investigator must document this in the site study records.

7.3. Lost to Follow Up

A participant will be considered lost to follow-up if he or she repeatedly fails to return for scheduled visits and is unable to be contacted by the study site.

The following actions must be taken if a participant fails to return to the clinic for a required study visit:

- The site must attempt to contact the participant and reschedule the missed visit as soon as possible and counsel the participant on the importance of maintaining the assigned visit schedule and ascertain whether or not the participant wishes to and/or should continue in the study.
- Before a participant is deemed lost to follow up, the investigator or designee must make every effort to regain contact with the participant (where possible, 3 telephone calls and, if necessary, a certified letter to the participant's last known mailing address or local equivalent methods). These contact attempts should be documented in the participant's medical record.
- Should the participant continue to be unreachable, he/she will be considered to have withdrawn from the study.

Discontinuation of specific sites or of the study as a whole are handled as part of [Appendix 1](#).

8. STUDY ASSESSMENTS AND PROCEDURES

- Study procedures and their timing are summarized in the SoA.

If these assessments are scheduled for the same nominal time, THEN the assessments should occur in the following order:

- 12-lead ECG
- vital signs
- blood draws.
- Protocol waivers or exemptions are not allowed
- Immediate safety concerns should be discussed with the sponsor immediately upon occurrence or awareness to determine if the participant should continue or discontinue study intervention.
- Adherence to the study design requirements, including those specified in the SoA, is essential and required for study conduct.
- All screening evaluations must be completed and reviewed to confirm that potential participants meet all eligibility criteria. The investigator will maintain a screening log to record details of all participants screened and to confirm eligibility or record reasons for screening failure, as applicable.
- Procedures conducted as part of the participant's routine clinical management (e.g., blood count) and obtained before signing of ICF may be utilized for screening or baseline purposes provided the procedure met the protocol-specified criteria and was performed within the time frame defined in the SoA.
- The maximum amount of blood collected from each participant over the duration of the study, including any extra assessments that may be required, will not exceed 500 mL
- Repeat or unscheduled samples may be taken for safety reasons or for technical issues with the samples.
- In Cohort 4b, participants will receive a topical NSAID or a topical steroid (high potency) as per the randomization schedule. These will be applied on Day -1 through to Day 5 after each subcutaneous abdominal injection.

